The primary objective of this study is to determine the infusion rate of Ang II that is necessary to return systolic blood pressure (SBP) to within 5% of baseline or greater in patients with essential hypertension taking ACE inhibitors, ARBs, or different classes of antihypertensive agents for greater than two months and further to determine the plasma levels of different RAAS components (as measured by the Attoquant system) in patients preoperatively, following induction, at a steady state infusion level of Ang II, and 30 minutes after surgical incision. In addition, a secondary objective is to determine how the levels of various RAAS components in the blood compare based on the method of analysis (liquid chromatography versus radioimmunoassay).

Methods and Measures

Design

Patients scheduled for general surgery who are evaluated in our preoperative assessment clinic (PAC) will be recruited for participation. Recruitment and consent for participation in the study will be performed prior to day of surgery via telephone screen or in person at the PAC. If patient is consented via telephone screen and agrees to participate, a consent form will be electronically mailed, or physically mailed to the patient. Patient will be asked to sign consent and return electronically or by physical mail. Patient will also sign consent in person on day of, prior to surgery. Once initial consent is received, (Giapreza) will be prepared and ready for use during surgery. Women of childbearing age will be asked about level of sexual activity and use of birth control. Given that the safety of Ang II has not been demonstrated in pregnant patients, the only women of childbearing age who will be considered for recruitment are those that (1) are not sexually active; or (2) are sexually active and use an acceptable method of birth control; or (3) are surgically sterile; or (4) are at least 2 years postmenopausal; or (5) have a monogamous partner who is surgically sterile; or (6) are practicing double barrier contraception. Once recruited, we will verify on the day of surgery that the patient is still agreeable to participate in the study.

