Women of childbearing age will be asked to undergo a pregnancy test on the day of surgery and provide a negative result. The determination of whether the patient takes their anti-hypertensive on the day of surgery will be determined by the PAC's normal practice and will be unaltered by this study. Our goal would be to enroll and obtain data on 15 patients for each group: (Arm 1) ACE group, (Arm 2) ARB group, and (Arm 3) patients on any other class of antihypertensive agent for greater than two months. There will also be a fourth comparison group (Arm 4) consisting of up to the first 15 enrolled patients whose SBP does not drop below the 80% baseline threshold after intubation. It would be our intent to continue enrolling patients until a sample size of 15 patients for each of the 3 groups (Arms 1,2,3) have completed the protocol and received the trial medication. Once each of the three experimental arms of the study (Arms 1,2,3) have 15 patients, enrollment in the fourth comparison group (Arm 4) will cease regardless of whether or not it has met the 15 patient goal. Based on an estimated incidence of hypotension of 40-60% following induction of anesthesia, we expect to have to consent approximately 90 patients. This is to account for patients who do not meet study criteria, thereby reaching our goal of 45 experimental patients and the tentative 15 patient comparison group.¹

There will be a total of 5 blood samples taken at three time points throughout the duration of the study. Patients will have an IV line placed in the holding area prior to surgery. At this time, we will draw the first two 10cc blood samples (one for LC/MS analysis, one for RIA analysis) for study purposes while the patient is in the preoperative holding room. The RIA labs will be processed at Wake Forest Baptist Medical Center and is sponsored by a grant from the NHLBI of the NIH. , and the LC/MS labs will be analyzed through an external contracted laboratory to gain information for RAAS component testing. An initial set of vital signs including heart rate (HR),

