Following intubation and before initial surgical incision, the BP will be checked using a non-invasive BP cuff every minute for 10 minutes. If a SBP that is less than 80% of the baseline reading is detected, the clinical team will immediately cycle the BP cuff in order to confirm the presence of hypotension. At this point an infusion of Ang II will be initiated at 2 ng/kg/min through a peripheral IV (although the recommended starting dose of Ang II is listed as 20ng/kg/min, this dosing regimen is based on patients in shock. The package insert also states that doses as low as 1.25ng/kg/min may be effective). Starting at a low dose will be important since patients taking ACE inhibitors may be more sensitive to Ang II. The BP will be checked every minute. The half-life of angiotensin 2 is < 1 minute and time to peak pharmacologic affect is less than 30-35 seconds so it will be necessary to monitor the blood pressure once per minute. The infusion will be increased at the discretion of the clinical team based on the response of the patient until a SBP within 5% of the baseline SBP has been achieved (although the rate will not be increased by more than 15ng/kg/min at a time and the rate will not exceed 80ng/kg/min based on the package insert dosing instructions). If the patient remains hypotensive despite use of the maximum dose of angiotensin II, then angiotensin II will be discontinued, the patient will be excluded from the study, and the blood pressure will be treated using conventional vasopressors. If a patient experiences SBP < 80% baseline for greater than four consecutive minutes after initiating Ang II, then a rescue vasopressor such as phenylephrine will be administered. This will be important for patients taking ARBs as they may be less sensitive to Ang II.

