Arm 3: Patients on any other antihypertensive medication, and must not be on an ACEi or ARB.

Arm 4: Patients who qualify for arm 1, 2, or 3 but whose SBP does not drop below 80% of baseline in the first 10 minutes after intubation.

- **Inclusion Criteria**

- Diagnosis of hypertension and treatment for greater than 2 months and on the following medications
 - ACE inhibitors, in addition they can also be on other classes of antihypertensive medication except for ARB
 - ARBs, in addition they can also be on other classes of antihypertensive medication except for ACEi
 - Any other antihypertensive medication, and must not be on an ACEi or ARB
- Patients undergoing general anesthesia
- American Society of Anesthesiologists physical status 1-3
- Age ≥ 40 given that hypertension is not prevalent below this age

- **Exclusion Criteria**

- American Society of Anesthesiologists physical status 4-6
- BMI > 40
- History of deep venous thrombosis / thromboembolic disease
- History of stroke,
- Baseline SBP of ≥ 160 mmHg,
- History of myocardial infarction or cardiac stents
- Difficult airway
- Asthma
- Diagnosis of congestive heart failure of any stage, regardless of preserved or reduced ejection fraction; this includes both systolic heart failure and diastolic heart failure;
- Diagnosis of chronic obstructive pulmonary disease of any stage; this includes diagnoses of chronic bronchitis and emphysema
- Pregnant patients (safety of Ang II in pregnancy is unknown)

- Patients at increased risk for venous thromboembolic events such as current diagnosis of cancer and/or diagnosis of blood clotting disorders
- **Sample Size**
Our goal would be to enroll and obtain data on 15 patients for each group: ACE group, ARB group, and patients on any other class of antihypertensive agent for greater than 2 months. In addition, we would like to obtain data for up to 15 patients in the comparison group (Arm 4). The sample size was chosen due to its similarity to the ATHOS II dose-finding trial.⁹ It would be our intent to continue enrolling patients until a sample size of 15 patients for all 3 experimental groups has been reached. Based on an estimated incidence of hypotension of 40-60%, we expect to have to consent approximately 90 patients.¹ This is not a multisite study.

Interventions and Interactions

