The primary outcome will be the mean dose required to increase the SBP in these 3 cohorts with essential hypertension (ACE inhibitor, ARB, or those on another class of hypertensive agents) to within 5% of baseline or higher. 15 patients will be selected to follow suit with other similar dose finding trials with vasopressors.¹⁰ The mean dose required to elevate SBP from the nadir to within 5% of baseline for each group will be compared for significance using a student's t-test and Bonferoni correction for multiple comparisons to determine if different doses of angiotensin 2 are required in patients chronically on ACE or ARB inhibitors. The dose-response data will be analyzed with linear regression to construct a dose response curve relating dose and percent increase in SBP from the nadir in the setting of general anesthesia. We will perform descriptive statistics on the patient population. Secondary outcomes will be the mean value for different components of the RAAS system in all 4 populations at different times prior to and during the surgical epoch;

Human Subjects Protection

Subject Recruitment Methods

Patients will be identified for participation in the Preoperative Assessment Clinic (PAC) prior to the day of surgery. Patients will be recruited by investigators and/or the study coordinator with the participation and collaboration of PAC attending and other staff present in the clinic involved in this study. We will attempt to recruit qualified subjects in a non-biased manner. Privacy will be protected because subjects will be recruited in the process of a confidential preoperative evaluation in the PAC. If they choose not participate no research record will be created other than to indicate that they declined to participate and as such there will be no contact information to destroy.

Informed Consent

Signed informed consent will be obtained from each subject. Research study members involved in the study will obtain informed consent. A copy of the signed consent will be given to the subject.

Confidentiality and Privacy

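### The planned per-arm mean does not show what proportion of patients are restored at a given infusion rate, and it covers completers only; add the median and the cumulative proportion at target on all patients who start the infusion

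*Combined protocol and SAP*

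**What the plan says.** The Objectives section sets out to "determine the infusion rate of Ang II that is necessary to return systolic blood pressure (SBP) to within 5% of baseline or greater". Under Outcome Measure(s) and Analytical Plan, "The primary outcome will be the mean dose required to increase the SBP in these 3 cohorts with essential hypertension". The arm means are compared by t-test with "Bonferoni correction for multiple comparisons to determine if different doses of angiotensin 2 are required". The dose-response data are to be "analyzed with linear regression to construct a dose response curve relating dose and percent increase in SBP from the nadir". No median, other quantile or proportion at target is planned for the required rate; the descriptive statistics mentioned there concern the patient population.

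Under Design, titration steps are at the clinical team's discretion, with the limits that "the rate will not be increased by more than 15ng/kg/min at a time and the rate will not exceed 80ng/kg/min". Rate and SBP are recorded every minute once an infusion starts, and a final rate is recorded 5 minutes after target is reached. A patient still hypotensive at the maximum rate is excluded from the study, and enrolment continues until "15 patients for each of the 3 groups (Arms 1,2,3) have completed the protocol and received the trial medication". Interventions and Interactions caps the infusion at 20 minutes. The plan does not say how a patient who meets that cap before target, or who receives a rescue vasopressor, enters the mean.

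**The concern.** Titrating each patient to a target yields a distribution of individual requirements. The objective asks which rate restores SBP, and a natural reading of that question is how many patients are at target by a given rate. A mean requirement does not say.

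The regression does not fill the gap. It models average percent rise from the nadir, whereas the target is defined against baseline. A nadir at 80% of baseline needs a rise of 95/80 − 1 = 19% to reach 95% of baseline; an assumed nadir of 60% needs 95/60 − 1 = 58%. The same percent rise is success in one patient and failure in another.

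The second issue is who is counted. Patients who fail at the ceiling have the highest requirements, and they leave the analysis and are replaced. At stake is whether the primary result of a dose-finding trial tells the reader how far it applies. The minute-by-minute record already holds what is needed.

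**Working it through.** **The plan's own figures.** "Based on an estimated incidence of hypotension of 40-60%, we expect to have to consent approximately 90 patients". Three arms of 15 need 45 hypotensive patients: 45/0.5 = 90, which reproduces at the midpoint; 45/0.6 = 75 and 45/0.4 = 113 (rounded up) are the ends of the stated range. At 50%, 90 × 0.5 = 45 leaves no room for failures at the ceiling. The 15 per arm has no calculation behind it: "The sample size was chosen due to its similarity to the ATHOS II dose-finding trial". No SD, effect size or power is stated.

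**Share needing more than the mean.** The spread of requirements is not in the documents, so I assume coefficients of variation (CV) of 0.3 to 1.5. For a log-normal requirement with σ = √ln(1 + CV²):

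- share above the mean = 1 − Φ(σ/2)
- median/mean = exp(−σ²/2)
- 90% rate/mean = exp(1.2816σ − σ²/2)

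| CV | σ | Share above mean | Median/mean | 90% rate/mean |
|---|---|---|---|---|
| 0.3 | 0.294 | 44% | 0.96 | 1.40 |
| 0.5 | 0.472 | 41% | 0.89 | 1.64 |
| 0.75 | 0.668 | 37% | 0.80 | 1.88 |
| 1.0 | 0.833 | 34% | 0.71 | 2.06 |
| 1.5 | 1.086 | 29% | 0.55 | 2.23 |

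If requirements are symmetric, the share is 50% at any spread. The point therefore does not depend on skew.

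**Effect of excluding failures at 80 ng/kg/min.** Take an illustrative true mean of 40 and CV 1.0: μ = ln 40 − 0.833²/2 = 3.342 and a = (ln 80 − 3.342)/0.833 = 1.249.

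- Excluded: 1 − Φ(1.249) = 10.6%.
- Completers' mean: 40 × Φ(1.249 − 0.833)/Φ(1.249) = 29.6.
- Share of all treated patients needing more than 29.6: 48%.

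With a true mean of 20 and CV 0.5, 0.08% are excluded and the mean is 19.9. The bias is therefore negligible when requirements lie well below the ceiling and material when they approach it.

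**What 15 patients per arm can support.**

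- Median: the 4th to 12th ordered values give a distribution-free interval with coverage 1 − 2 × P(Bin(15, 0.5) ≤ 3) = 1 − 2 × 576/32768 = 96.5%.
- 90% rate, distribution-free: P(all 15 lie below it) = 0.9^15 = 0.206, so there is no 95% upper limit. A one-sided limit needs 29 patients.
- 90% rate, log-normal (noncentral t): the ratio of upper to lower 95% limit is 2.1, 2.8 and 3.6 at CV 0.5, 0.75 and 1.0. With an assumed median of 10 ng/kg/min and log-SD 0.7, the estimate is 10 × exp(1.2816 × 0.7) = 24.5, with an interval of about 17 to 49.
- With failures kept: if 2 of 17 treated patients in an arm fail at the ceiling, 2/17 = 11.8% exceeds 10%, and that arm's 90% rate lies above the tested range.

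These precision figures treat each requirement as known exactly. Discretionary steps of up to 15 ng/kg/min only bracket it, so real intervals will be wider.

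**The case against.** The best defence is that the mean is fit for its planned use. It is compared between arms to see whether patients on ACE inhibitors or ARBs need different doses, and a difference in means addresses that. A mean individual requirement is also one legitimate answer to the objective. This stands, and it is why the mean should stay.

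Some patients exceed any central summary, and half exceed the median by definition. That is true, but the median carries its proportion with it, and the cumulative curve supplies the proportion at every other rate.

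The size is assumed, and starting and maximum rates do not prove skew. For an assumed median of 10 and log-SD of 0.5 to 1.0, the mean exceeds the median by 1.3 to 6.5 ng/kg/min, less than one permitted step of 15. This also stands: the case rests on the missing proportion and the excluded failures, not on a demonstrated gap between mean and median.

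Quantiles computed from completers would share the mean's downward bias. That is right, and it means the analysis set must change along with the summary.

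**Conclusion.** The point holds as a gap in the analysis that is cheap to close. As planned, neither the mean nor the regression gives the proportion of patients restored at a given rate. Under the assumed spreads, roughly 30% to 50% of patients would need more than the mean, and the completers-only mean is biased low by an amount that depends on how close requirements come to the ceiling.

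A reader might infer more, and the documents do not support it:

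- **That the mean is the chosen dose, to be given to everyone.** The plan never says so, and the protocol titrates each patient individually.
- **That the trial fails to answer its own question, or that a known share of patients would be under-dosed.** The mean is a partial answer, and with no SD given the share is a range under assumption.
- **That the data will readily yield a rate that works for 90% in each arm.** Fifteen patients give no distribution-free 95% upper limit, and the parametric interval spans about a two- to nearly fourfold range.

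**What to change.** Amend the Analytical Plan text only; keep the mean, the t-tests and the regression.

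1. Per arm, add the median required rate (the rate at which 50% reach target) with a 95% interval, and the cumulative proportion at target by rate.
2. Base these on all patients who start the infusion. Say that a patient excluded under Design for failure at the maximum rate still contributes the data recorded up to that point.
3. Treat patients who do not reach target (failure at the maximum rate, time cap, rescue vasopressor) as right-censored at the highest rate given without reaching target. Treat the others as interval-censored between the last rate not at target and the first at target; the lower limit is zero for those at target on the starting rate. A Turnbull estimate or an interval-censored log-normal model would serve. Rescue and the time cap may be related to the requirement itself, so add a sensitivity analysis for those patients.
4. State which recorded rate counts as the requirement: the first to reach target, or the one recorded 5 minutes later. They can differ, because Design allows the infusion to be reduced or halted if SBP overshoots.
5. Report the 90% rate as exploratory, preferably from one model over the 45 or more treated patients with arm as a covariate, and say so when it lies above the tested range.

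No new data or visits are needed, and titration, rescue and stopping rules are untouched. The cost is a little more analysis and wide intervals, which the report should show.

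### The between-arm contrasts are not named, and a step-down on the same t-tests would recover power that plain Bonferroni gives up; this is an efficiency gain, not the correction of an error

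*Combined protocol and SAP*

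**What the plan says.** The Analytical Plan defines the outcome: "The primary outcome will be the mean dose required to increase the SBP in these 3 cohorts with essential hypertension". For the comparison between arms it says the mean dose "for each group will be compared for significance using a student's t-test and Bonferoni correction for multiple comparisons", and gives the purpose as "to determine if different doses of angiotensin 2 are required in patients chronically on ACE or ARB inhibitors". It does not list the contrasts, count them, or state alpha or sidedness, and it mentions no step-down procedure.

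The arm size rests on precedent. Under Sample Size: "The sample size was chosen due to its similarity to the ATHOS II dose-finding trial". No power calculation, effect size or SD is given anywhere.

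Two remarks in Design bear on direction. One is that "patients taking ACE inhibitors may be more sensitive to Ang II", given as the reason for a low starting rate. The other, attached to the rescue rule, is "This will be important for patients taking ARBs as they may be less sensitive to Ang II". The Background section says it is not known whether patients on these drugs respond differently from patients who are not.

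**The concern.** A Bonferroni cut-off is undefined until the number of comparisons is fixed. The stated purpose, and the Background's contrast with patients not on these drugs, fit two contrasts best: ACE vs other and ARB vs other. The words about comparing each group also allow all three pairs. If the family were chosen after the data are seen, the cut-off could follow the result.

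The second issue is efficiency. The trial asks about two drug classes. Bonferroni holds the second contrast to the strict cut-off even after the first has been shown. With 15 per arm, that lowers the chance of answering both questions, and the same p-values could be used at no cost in type I error.

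**Working it through.** **Plan's own figures.** There is no power figure to reproduce. The only related arithmetic is about 90 consents for 45 treated patients (45/0.5 = 90 at the midpoint of 40-60% incidence), and it does not bear on this point.

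**Inputs.** From the documents: 15 per arm in Arms 1 to 3, two-arm Student's t-tests (28 df), a starting rate of 2 and a maximum of 80 ng/kg/min. Assumed, because the documents are silent: familywise alpha 0.05 two-sided, and the effect sizes and SDs below.

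**Effect of the cut-off alone.** Power for one contrast comes from the noncentral t with δ = d√(n/2). At d = 1.0 SD, δ = √7.5 = 2.74. Power is 75% at 0.05, 65% at 0.025 and 58% at 0.0167. The difference detectable with 80% power is 1.06, 1.18 and 1.25 SD respectively. The unstated family size alone therefore moves power by about 7 points at d = 1.0.

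**Why step-down is safe.** Holm compares the smallest p with 0.05/m, the next with 0.05/(m−1), and so on, stopping at the first failure. Every cut-off is at least 0.05/m, so no Bonferroni rejection is lost, and the familywise error stays controlled. With three pairwise means, once one pair truly differs at most one other pair can be equal. Shaffer's version therefore tests the remaining two at 0.05 after the smallest p passes 0.0167.

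**Size of the gain.** 400,000 simulated trials per case; log-normal dose need; pooled t-tests on raw dose; values below 2 set to 2. Excluded means that values above 80 are redrawn until 15 complete; capped means that they are set to 80. Figures are power in %, A = ACE vs other, R = ARB vs other.

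| Medians ACE/other/ARB, log SD | Two contrasts: Bonferroni → Holm | Three pairs |
|---|---|---|
| 10/20/40, 0.8, excluded | A 39→43, R 34→38, both 8→15 | Bonferroni/Holm/Shaffer: A 33/43/51, R 28/37/44, both 5/15/17 |
| 10/20/40, 0.8, capped | A 42→48, R 47→52, both 14→24 | A 35/47/55, R 41/52/59, both 9/24/26 |
| 10/20/40, 0.6, excluded | A 70→78, R 65→73, both 41→57 | Bonferroni→Shaffer: A 63→80, R 59→76 |
| 10/20/40, 1.0, excluded | A 22→23, R 19→20, both 1.5→3.6 | A 18→30, R 15→25 |
| 10/15/25, 0.8, excluded | A 13→14, R 21→21 | A 10→20, R 16→26 |
| 10/20/20, 0.8, excluded | A 39→39 | Bonferroni/Holm/Shaffer, each true pair: 33/35/40 |
| 20/20/40, 0.8, excluded | R 34→34 | each true pair: 28/30/34 |

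In the first row the chance of at least one finding is 65% (two contrasts) or 92% (three pairs) under every rule; it is unchanged in all cases. Step-down familywise error was 4.0-4.4% with all arms equal and 2.4-4.9% with one pair equal. No Bonferroni rejection was lost.

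**Check under another model.** With normal data, equal SDs and opposite shifts of 0.8, 1.0 or 1.2 SD, two contrasts go from 44, 65 and 81% to 49, 72 and 88% each, and both shown from 13, 36 and 64% to 23, 52 and 77%. With one arm shifted by 1.0 SD, two contrasts gain 0.1 point (64.6% to 64.7%). Three pairs under Shaffer gain about 8.5 (58.1% to 66.6%).

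**Interval width.** t(28) quantiles are 2.048 unadjusted, 2.368 for two contrasts and 2.546 for three. The ratios are 2.368/2.048 = 1.16 and 2.546/2.048 = 1.24.

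**The case against.** Bonferroni is valid, familiar and comes with matching simultaneous intervals, which suits an outcome that is a mean dose. Under the two-contrast reading the gain per contrast is small, and even with Holm about 85% of trials at the base assumptions (excluded) would not show both differences. Arm size limits this trial far more than the choice of correction. All of that stands and sets the priority low.

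Three stronger readings are tempting, and the documents do not support them.

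- A reader might infer that the protocol expects opposite shifts in the ACE and ARB arms. It says only that they may occur, in sentences that explain the starting rate and the rescue rule, and the Background calls the response unknown. The opposite-shift case is one scenario, not a design assumption.
- A reader might call the single-contrast gain modest throughout. That fits two contrasts. With three pairs and both arms shifted it is about 9 to 20 points at the base assumptions.
- A reader might take the exclusion model as the protocol's own rule. Design covers a patient still hypotensive at the maximum rate ("the patient will be excluded from the study, and the blood pressure will be treated using conventional vasopressors"), and enrolment then continues ("It would be our intent to continue enrolling patients until a sample size of 15 patients for each of the 3 groups"). Patients between 80% of baseline and the 95% target at that rate are not clearly covered. The model also leaves out discretionary titration, rescue vasopressor and the 20-minute limit. The capped results show how far this matters.

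None of this touches two facts: the contrasts are unnamed, and on the same p-values step-down rejects everything that Bonferroni rejects.

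**Conclusion.** The point holds as a cheap improvement, to be considered. A reader might infer that the planned analysis is wrong or inflates error. It does not, because Bonferroni controls the familywise error.

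The size depends on assumed effects. If both arms differ in opposite directions (medians 10/20/40, log SD 0.8), two contrasts gain about 4 to 6 points each, with a range of about 1 to 8 across the both-arms-shifted cases tried. Both shown rises from 8% to 15% with exclusion, or from 14% to 24% with capping. With three pairs, the contrasts against other gain about 9 to 13 points with Holm and 16 to 20 with Shaffer (differences taken before rounding). If only one arm differs, the gain is close to nil with two contrasts and up to about 7 points with three pairs (about 8.5 in the normal-data check). The chance of at least one finding is the same under every rule, so step-down does not make up for the small arms.

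**What to change.** In the Analytical Plan, name the contrasts, the familywise alpha and the sidedness in advance. Keep the t-tests on mean dose and test them step-down:

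- ACE vs other and ARB vs other (closest to the stated purpose): Holm, 0.025 then 0.05.
- All three pairs: Holm, 0.0167/0.025/0.05; or Shaffer, 0.0167 for the smallest p and, if it passes, 0.05 for each of the other two.

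Report Bonferroni-adjusted intervals for the mean differences beside the tests, and state in advance that the step-down test decides the claim.

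The cost is a few sentences, with no new data or tests. The real downside is that step-down has no simple matching simultaneous intervals. A pair that passes only at a later step can have an adjusted interval that includes zero. This happens exactly as often as the power gain for that pair, for example in about 4% of trials per contrast with two contrasts at 10/20/40 with exclusion. If the study team prefers matching intervals and keeps Bonferroni, that is defensible, but the contrasts still need to be named.
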